5.8.3. Clinical Laboratory Measurements

Individual participant laboratory parameter measurements will be evaluated by PCSV criteria (See [Appendix 10.1](#)), specifically identifying participants with at least one post-baseline measurement that meets the PCSV criteria. These laboratory parameters will be presented by the biological functions (e.g. red blood cells and platelets, white blood cells, and liver function, etc.). The incidence of PCSVs at any time including data from unscheduled visits during the study period will be summarized.

Listings of laboratory measurements at all timepoints for the participants that meet PCSV criteria will be provided. Listings of all local laboratory measurements will also be provided.

A listing of all women of childbearing potential with a confirmed serum pregnancy test during the study will be provided.

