WBC	<3.0 Giga/L or <LLN (if LLN ≤3.0 Giga/L) and baseline ≥3.0 Giga/L or ≥LLN (if LLN≤3.0 Giga/L) (Non-Black); <2.0 Giga/L or <LLN (if LLN ≤2.0 Giga/L) and baseline ≥2.0 Giga/L or ≥LLN (if LLN≤2.0 Giga/L) (Black) ≥16.0 Giga/L or ≥ULN (if ULN ≥16.0 Giga/L) and baseline < 16 Giga/L or <ULN (if ULN ≥16.0 Giga/L)	
Lymphocytes	>4.0 Giga/L or >ULN (if ULN ≥4.0 Giga/L) and baseline ≤4.0 Giga/L or ≤ULN (if ULN ≥4.0 Giga/L)	
Neutrophils	<1.5 Giga/L or <LLN (if LLN ≤1.5 Giga/L) and baseline ≥1.5 Giga/L or ≥LLN (if LLN ≤1.5 Giga/L) (Non-Black); <1.0 Giga/L or <LLN (if LLN ≤1.0 Giga/L) and baseline ≥1.0 Giga/L or ≥LLN (if LLN ≤1.0 Giga/L) (Black)	
Monocytes	>0.7 Giga/L or >ULN (if ULN ≥0.7 Giga/L) and baseline ≤0.7 Giga/L or ≤ULN (if ULN ≥0.7 Giga/L)	
Basophils	>0.1 Giga/L or >ULN (if ULN ≥0.1 Giga/L) and baseline ≤0.1 Giga/L or ≤ULN (if ULN ≥0.1 Giga/L)	
Eosinophils	>0.5 Giga/L or >ULN (if ULN ≥0.5 Giga/L) and baseline ≤0.5 Giga/L or ≤ULN (if ULN ≥0.5 Giga/L)	

Parameter	PCSV	Comments
Hemoglobin	
≤ 115 g/L or \leqLLN (if LLN ≤ 115 g/L) and baseline > 115 g/L or $>$LLN (if LLN ≤ 115 g/L) for male; ≤ 95 g/L or \leqLLN (if LLN ≤ 95 g/L) and baseline > 95 g/L or $>$LLN (if LLN ≤ 95 g/L) for Female.
 
≥ 185 g/L or \geqULN (if ULN ≥ 185 g/L) and baseline < 185 g/L or $<$ULN (if ULN ≥ 185 g/L) for Male; ≥ 165 g/L or \geqULN (if ULN ≥ 165 g/L) and baseline < 165 g/L or $<$ULN (if ULN ≥ 165 g/L) for Female
 
Decrease from Baseline ≥ 20 g/L
	Three criteria are independent.
Hematocrit	
≤ 0.37 v/v or \leqLLN (if LLN ≤ 0.37 v/v) and baseline > 0.37 v/v or $>$LLN (if LLN ≤ 0.37 v/v) for Male; ≤ 0.32 v/v or \leqLLN (if LLN ≤ 0.32 v/v) and baseline > 0.32 v/v or $>$LLN (if LLN ≤ 0.32 v/v) for Female
 
≥ 0.55 v/v or \geqULN (if ULN ≥ 0.55 v/v) and baseline < 0.55 v/v or $<$ULN (if ULN ≥ 0.55 v/v) for Male; ≥ 0.5 v/v or \geqULN (if ULN ≥ 0.5 v/v) and baseline < 0.5 v/v or $<$ULN (if ULN ≥ 0.5 v/v) for Female
	Two Criteria are independent
RBC	≥ 6 Tera/L or \geq ULN (if ULN ≥ 6 Tera/L) and baseline < 6 Tera/L or $<$ ULN (if ULN ≥ 6 Tera/L)	
Platelets	
< 100 Giga/L or $<$LLN (if LLN ≤ 100 Giga/L) and baseline ≥ 100 Giga/L or \geqLLN (if LLN ≤ 100 Giga/L)
 
≥ 700 Giga/L or \geqULN (if ULN ≥ 700 Giga/L) and baseline < 700 Giga/L or $<$ULN (if ULN ≥ 700 Giga/L)
	Two independent criteria

Parameter	PCSV	Comments
Vital signs		
HR	<45 bpm and decrease from baseline \geq 20 bpm \geq 120 bpm and increase from baseline \geq 20 bpm	

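### SAP 10.1 gives boys and girls under 12 different hemoglobin and hematocrit PCSV limits, so the flag can depend on sex when value, baseline and laboratory range are identical

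*SAP*

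**What the plan says.** The laboratory analysis in SAP 5.8.3 works by "specifically identifying participants with at least one post-baseline measurement that meets the PCSV criteria". It summarizes PCSV incidence and lists all laboratory measurements for participants who meet a criterion. SAP 5 displays summaries by body weight group and for all participants combined, not by sex.

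The limits are in SAP 10.1:

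- **Hemoglobin, low.** Males: at or below 115 g/L, with the alternative "LLN (if LLN ≤ 115 g/L) for male". Females: at or below 95 g/L, with the alternative "LLN (if LLN ≤ 95 g/L) for Female". Baseline must lie above the limit.
- **Hemoglobin, high.** 185 g/L for males, 165 g/L for females.
- **Hemoglobin, change.** "Decrease from Baseline ≥ 20 g/L", the same for both sexes. The comment on the row is "Three criteria are independent".
- **Hematocrit, low.** Males 0.37, with the alternative "LLN (if LLN ≤ 0.37 v/v) for Male". Females 0.32, with the alternative "LLN (if LLN ≤ 0.32 v/v) for Female".
- **Hematocrit, high.** 0.55 for males, 0.50 for females. The comment is "Two Criteria are independent". There is no change criterion.

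SAP 6.3 uses the fixed threshold when the normal range is missing. SAP 10.1 drops the baseline condition when baseline is missing. Protocol 9.2.5 sends hematology to local laboratories. Neither document gives an LLN or ULN value.

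**The concern.** The split is applied to a population that is entirely under 12, and the SAP neither justifies it nor adapts it to age. The creatinine row of the same appendix labels its fixed limit as an adult one, which suggests that the table was not built for this study.

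Because the tables are not broken down by sex, each hemoglobin or hematocrit percentage pools two definitions of the event. In groups planned at 12 or more children, the count then reflects how many boys and girls the group contains as well as what happened to their blood counts. Hemoglobin matters here: the qualifying conditions in Protocol 7.2.1 include sickle cell anemia, thalassemia and cancer treatment.

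**Working it through.** The plan gives no figure to reproduce. The check applies the rule to a boy and a girl with the same data, then asks how often the flags differ.

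**Step 1: the limit in force.** The LLN clause can be read in two ways.

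- *Override:* the LLN replaces the fixed threshold T when LLN ≤ T, so the limit is L = min(T, LLN), and L = T if the LLN is missing. This fits the missing-range rule in SAP 6.3.
- *Literal OR:* either condition flags. The LLN clause then adds nothing on the low side, and L = T always.

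On the override reading (LLN values assumed):

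| Local LLN | Boy's limit | Girl's limit |
|---|---|---|
| Hb ≤95 g/L | LLN | LLN |
| Hb 100 g/L | 100 | 95 |
| Hb 110 g/L | 110 | 95 |
| Hb ≥115 g/L or missing | 115 | 95 |
| Hct ≤0.32 | LLN | LLN |
| Hct 0.34 | 0.34 | 0.32 |
| Hct ≥0.37 or missing | 0.37 | 0.32 |

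On the literal reading the limits are 115/95 g/L and 0.37/0.32 at every LLN. On the high side the override gives max(T, ULN), so girls have the lower limit whenever the ULN is below 185 g/L or 0.55, or is missing.

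**Step 2: identical children, override reading, LLN 110 g/L (Hct 0.34) assumed.** The low flag needs value ≤ L and baseline > L.

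- Hb 118 to 105 (fall 13): boy flagged (105 ≤ 110, 118 > 110); girl not (105 > 95).
- Hb 126 to 105 (fall 21): both flagged, because the girl meets the 20 g/L fall.
- Hb 105 to 94 (fall 11): girl flagged (94 ≤ 95, 105 > 95); boy not, because his baseline of 105 is not above 110.
- Hct 0.36 to 0.33: boy flagged; girl not, and no change criterion can catch it.

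The disagreement therefore runs both ways.

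**Step 3: flag rates with no drug effect.** Assume baseline B ~ N(μ, σ), an independent change D ~ N(0, 7) g/L, one post-baseline value and LLN 110. Then

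P(low flag) = P(B > L and B + D ≤ L) = ∫ from L to ∞ of f(b) · Φ((L − b)/7) db,

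where f is the baseline density, with L = 110 for boys and L = 95 for girls.

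| Baseline mean (SD), g/L | Boys | Girls |
|---|---|---|
| 120 (10) | 9.0% | 1.6% |
| 120 (12) | 8.0% | 2.3% |
| 110 (12) | 8.4% | 6.2% |
| 105 (12) | 6.8% | 8.0% |
| 100 (12) | 4.6% | 8.9% |

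At mean 120 (SD 10), moving the LLN from 105 to 115 takes the boys' rate from about 6.2% to 10.5%; the girls' rate stays at 1.6%. Counting the fall of 20 g/L or more as well changes little: 9.1% vs 1.8% at LLN 110.

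**Step 4: effect on a weight group.** Take 14 children (half of 28, an assumed even split).

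- Mean 120 (SD 10), 10 boys and 4 girls: (10 × 9.0 + 4 × 1.6)/14 = 6.9%. With 4 boys and 10 girls: (4 × 9.0 + 10 × 1.6)/14 = 3.7%.
- Mean 100 (SD 12), the same two mixes: (10 × 4.6 + 4 × 8.9)/14 = 5.8% and (4 × 4.6 + 10 × 8.9)/14 = 7.7%.
- Extremes at mean 120: 14 × 0.090 = 1.3 expected flags if all are boys, and 14 × 0.016 = 0.2 if all are girls.

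**The case against.** A reader might infer that the rule systematically under-detects falls in girls. The documents do not support that. It holds if children start with near-normal hemoglobin, but the baseline condition bars a boy who starts at or below his limit from the low criterion, and many eligible conditions lower hemoglobin. In Step 3 the difference shrinks and then reverses as the baseline mean falls. No baseline distribution is given, so the direction is unknown.

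A reader might also blame the way the LLN can only make a limit more extreme. The same convention runs through most of the appendix (sodium, potassium, chloride, albumin, white cells, platelets and others), so it is not a defect of these two rows. Replacing the limits with the LLN itself would turn a potentially clinically significant value into a merely abnormal one and tie the flag to each site's range. That is a trade-off, not a correction.

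The safeguards are real. A fall of 20 g/L or more flags either sex for hemoglobin. SAP 5.8.3 lists every local laboratory value. Protocol 9.2.5 requires investigator review and repetition of significantly abnormal results. Protocol 11.4.3.2 also plans change-from-baseline laboratory summaries, which the SAP does not list among its modifications, so PCSV incidence is not the only planned laboratory summary. The study is single-arm and descriptive, with little routine post-baseline hematology and no comparison between the sexes.

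These arguments limit the consequence. None explains why the same value, baseline and LLN should count as an event in one child under 12 and not in another because of sex.

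**Conclusion.** The sex split should be removed from the hemoglobin and hematocrit rows. That identical data can be classified differently follows from the text alone. On the override reading it needs, on the low side, a local LLN above 95 g/L or 0.32, or a missing LLN; on the literal reading it is always possible.

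The size depends on assumptions the documents do not supply: LLN, baseline distribution and change SD. Over the scenarios at LLN 110, boys vs girls run from 9.0% vs 1.6% to 4.6% vs 8.9%. For a group of 14, that amounts to about one expected flag between an all-boy and an all-girl group at mean 120, and less for ordinary mixes. A missed flag means absence from the PCSV count and the PCSV listing, not an unseen value. This is a minor-to-moderate correction to a safety summary.

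**What to change.** In the hemoglobin and hematocrit rows of SAP 10.1, replace the male and female limits with one sex-neutral set of low and high limits suited to the study's age range, chosen and justified by the sponsor's clinical team. Keep the existing LLN/ULN override and the baseline condition. Use the common limit when the normal range is missing. Keep the independent hemoglobin fall of 20 g/L or more.

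With a common threshold T the low limit is min(T, LLN) for both sexes, so identical data always give the same flag. Any remaining difference by sex would come from the laboratory's own reference range.

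The cost is two appendix rows and minor programming, with no new data. Counts for these rows will no longer match the sponsor's standard PCSV table in other studies, and a footnote should say so.

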6.3. Data Handling Convention for Missing Data

Missing data will not be imputed in listings. This section includes the methods for missing data imputation for some summary analyses, if necessary.

For categorical variables, participants with missing data are not included in calculations of percentages unless otherwise specified. When relevant, the number of participants with missing data is presented.

Adverse event

If the severity of a TEAE is missing, it will be classified as “severe” or “Grade 3” in the frequency tables by intensity of TEAEs. If the assessment of relationship of a TEAE to the investigational product is missing, it will be classified as related to the investigational product.

Medication/Procedure

If a medication date or time is missing or partially missing and it cannot be determined whether it was taken prior or concomitantly or stopped prior to the first study treatment administration, it will be considered as concomitant medication/procedure by imputing the start date on the date of first study treatment administration.

Potentially Clinically Significant Value (PCSV)

For PCSVs with 2 conditions, one based on a change from baseline value and the other on a threshold value or a normal range, with the first condition being missing, the PCSV will be based only on the second condition.

For a PCSV defined on a threshold and/or a normal range, this PCSV will be derived using this threshold if the normal range is missing; e.g., for eosinophils the PCSV is >0.5 giga/L or $>\text{ULN}$ if $\text{ULN} \geq 0.5$ giga/L. When ULN is missing, the value 0.5 should be used.

Measurements flagged as invalid by the laboratory will not be summarized or taken into account in the computation of PCSVs.

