10. APPENDIX

10.1. Criteria for Potentially Clinically Significant Values (PCSV)

If baseline is missing, only post-baseline criteria will be considered.

Parameter	PCSV	Comments
Clinical chemistry		
ALT	>3 and \leq 5 ULN and baseline \leq 3 ULN >5 and \leq 10 ULN and baseline \leq 5 ULN >10 and \leq 20 ULN and baseline \leq 10 ULN >20 ULN and baseline \leq 20 ULN	Enzymes activities must be expressed in ULN, not in IU/L. Each category is calculated independently.
AST	>3 and \leq 5 ULN and baseline \leq 3 ULN >5 and \leq 10 ULN and baseline \leq 5 ULN >10 and \leq 20 ULN and baseline \leq 10 ULN >20 ULN and baseline \leq 20 ULN	Enzymes activities must be expressed in ULN, not in IU/L. Each category is calculated independently.
Alkaline Phosphatase	>1.5 ULN and baseline \leq 1.5 ULN	Enzymes activities must be expressed in ULN, not in IU/L.
Total Bilirubin	>1.5 and \leq 2 ULN and baseline \leq 1.5 ULN >2 ULN and baseline \leq 2.0 ULN	Must be expressed in ULN, not in μ mol/L or mg/L.
Conjugated bilirubin	>35% Total Bilirubin and TBILI >1.5 ULN, and baseline Total Bilirubin \leq 35% or TBILI \leq 1.5 ULN	Conjugated bilirubin dosed on a case-by-case basis
ALT and Total Bilirubin	ALT > 3 ULN and TBILI > 2 ULN, and baseline ALT \leq 3 ULN or TBILI \leq 2 ULN	

Parameter	PCSV	Comments
CPK	>3 and \leq 10 ULN and baseline \leq 3ULN >10 ULN and baseline \leq 10ULN	
Creatinine	\geq 150 μ mol/L (Adults) or \geq ULN (if ULN \geq 150 μ mol/L) and baseline $<$ 150 μ mol/L or $<$ ULN (if ULN \geq 150 μ mol/L) \geq 30% change from baseline \geq 100% change from baseline	3 independent criteria
Creatinine Clearance (Cockcroft's formula)	<15 ml/min and baseline \geq 15 ml/min (end stage renal impairment) \geq 15 to <30 ml/min and baseline \geq 30 ml/min (severe renal impairment) \geq 30 to < 60 ml/min and baseline \geq 60 ml/min (moderate renal impairment) \geq 60 to < 90 ml/min and baseline \geq 90 ml/min (mild renal impairment)	Four independent criteria
Uric Acid		Two independent criteria
Hyperuricemia:	>408 μ mol/L or >ULN (if ULN \geq 408 μ mol/L) and baseline \leq 408 μ mol/L or \leq ULN (if ULN \geq 408 μ mol/L)	
Hypouricemia:	<120 μ mol/L or <LLN (if LLN \leq 120 μ mol/L) and baseline \geq 120 μ mol/L or \geq LLN (if LLN \leq 120 μ mol/L)	
Blood Urea Nitrogen	\geq 17 mmol/L or \geq ULN (if ULN \geq 17 mmol/L) and baseline <17 mmol/L or <ULN (if ULN \geq 17 mmol/L)	Two independent criteria
Chloride		Two independent criteria

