SBP	\leq 95 mmHg and decrease from baseline \geq 20 mmHg \geq 160 mmHg and increase from baseline \geq 20 mmHg	
DBP	\leq 45 mmHg and decrease from baseline \geq 10 mmHg \geq 110 mmHg and increase from baseline \geq 10 mmHg	

Footnote: Only data collected in this study will be applied to these criteria.

Signature Page for VV-RIM-00192515 v1.0

Approval/eSignature	 2022 13:11:23 GMT+0000
Approval/eSignature	 00
Approval/eSignature	 22 15:42:27 GMT+0000
Approval/eSignature	 22 19:51:37 GMT+0000
Approval/eSignature	 00

Signature Page for VV-RIM-00192515 v1.0 Approved

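### SAP Appendix 10.1 sets one HR, SBP and DBP flag limit for every child of 3 to <40 kg, so at high resting HR or low resting BP only the change condition filters

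*SAP*

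**What the plan says.** Protocol 7.2.1 admits children under 12 years weighing 3 to <40 kg. SAP 5.8.4 sends vital signs to the PCSV criteria of Appendix 10.1 and lists all measurements for any participant who meets one. (Its first sentence speaks of laboratory parameters, but the section heading and the listings make the intent plain.)

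Each vital-sign flag in Appendix 10.1 joins an absolute limit and a change from baseline, and both must hold:

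- HR high: at least "120 bpm and increase from baseline" of at least 20 bpm.
- HR low: "<45 bpm and decrease from baseline" of at least 20 bpm.
- SBP low: at or below "95 mmHg and decrease from baseline" of at least 20 mmHg.
- SBP high: at least "160 mmHg and increase from baseline" of at least 20 mmHg.
- DBP low: at or below "45 mmHg and decrease from baseline" of at least 10 mmHg.
- DBP high: at least 110 mmHg, with a rise of at least 10 mmHg.

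No row has an age or weight band. SAP section 5 defines dosing subgroups A1, A2, B1 and B2, but the limits do not use them. Several laboratory rows vary by sex or race, or give way to the local reference range; the lymphocyte row, for instance, contains "4.0 Giga/L or >ULN (if ULN" followed by a condition on the size of the ULN. The vital-sign rows have nothing similar. For a missing baseline, the appendix says "If baseline is missing, only post-baseline criteria will be considered", and SAP 6.3 agrees.

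**The concern.** A two-part flag works when each part does something: the absolute limit says that the reading is unusual, and the change condition says that it is new. A fixed absolute limit can do that only if it lies in a sensible place relative to the child's resting value. Over a weight range of 3 to <40 kg, a single limit may lie on the wrong side of the usual reading for some children.

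Where that happens, the flag in one direction becomes a plain change rule, and the flag in the other direction becomes very hard to reach. The same label would then mean different things for different children, and the PCSV listing in SAP 5.8.4 would be chosen partly by resting level. Safety and tolerability is a secondary objective, and vital signs are taken about 1 hour after dosing (Protocol 9.1.1, footnote 9), so the flags should screen consistently.

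**Working it through.** **1. Where the absolute limit stops mattering (exact, from the table).** With recorded baseline B, a high flag needs a rise of max(change limit, absolute limit − B). A low flag needs a fall of max(change limit, B − absolute limit). The absolute limit is redundant when the change limit is the larger term.

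- High HR: 120 − B ≤ 20, so B ≥ 120 − 20 = 100 bpm.
- Low SBP: B − 95 ≤ 20, so B ≤ 95 + 20 = 115 mmHg.
- Low DBP: B − 45 ≤ 10, so B ≤ 45 + 10 = 55 mmHg.

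Beyond these points only the change of 20 bpm, 20 mmHg or 10 mmHg filters.

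**2. The opposite flags (exact).**

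- Low HR from 130: a fall of more than 130 − 45 = 85 bpm.
- High SBP from 90: a rise of 160 − 90 = 70 mmHg.
- High DBP from 55: a rise of 110 − 55 = 55 mmHg.

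**3. How often a stable child would be flagged (assumption).** The documents give neither resting values nor within-child SDs, so both are shown as ranges. The baseline and two post-baseline readings (1 hour and day 29, as Protocol Table 3 reads) are taken as independent N(μ, SD). Then P(at least one flag) = E over B of [1 − (1 − p(B))²], where p(B) = P(Y ≥ max(120, B + 20)) for high HR and P(Y ≤ min(95, B − 20)) for low SBP.

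| Flag | Assumed mean | SD | Chance of a flag |
|---|---|---|---|
| High HR | 75 | 15 | 0.26% |
| High HR | 90 | 8-15 | 0.02-3.8% |
| High HR | 100 | 8-15 | 0.8-11.6% |
| High HR | 110-150 | 8-15 | 4.8-27.5% |
| Low SBP | 120 | 6-10 | 1.0% or less |
| Low SBP | 110 | 6-10 | 0.4-6.1% |
| Low SBP | 80-100 | 6-10 | 1.6-13.4% |

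If the pre-dose and 1-hour readings correlate at 0.3-0.7, with day 29 independent, the ranges for HR means 110-150 and SBP means 80-100 fall to 2.5-25.2% and 0.8-11.1%.

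**4. How much the absolute limit still filters (same model, one post-baseline reading).** The share of qualifying changes that also pass the absolute limit is P(limit and change) / P(change).

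- HR, SD 8-15: 64-68% at mean 110, 91-98% at 120, 99-100% at 130.
- SBP, SD 6-10: 99-100% at means 80-90, 86-93% at 100, 21-40% at 110.
- DBP, SD 5-10: 18-45% at mean 55, 2-23% at 60.

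The share at HR mean 110 is below 100% although 110 exceeds the break-even of 100. A 20 bpm rise is likelier after a baseline reading that happened to be low, and some of those lie under 100. At DBP means of 55-60 the 45 mmHg limit still removes most qualifying falls, so no DBP flag rate is claimed.

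**5. Chance of catching a real change the other way (per reading, assumed SDs as in step 3).** A true fall of 40 bpm from HR 130 crosses the low limit 0.14% of the time or less, and a fall of 60 bpm 0.1-4.8%. A true rise of 40 mmHg from SBP 90 crosses the high limit 0.14% or less, and a rise of 50 mmHg 0.04-2.3%.

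**The case against.** The strongest reply is that very little depends on these flags. Protocol 11.4.3.2 asks for PCSV counts for laboratory tests only; for vital signs it asks for baseline and change-from-baseline summaries. SAP 5.8.4 states no incidence table for vital signs, and it lists vital signs for every participant next to the flagged listing. Investigators appraise vital signs for adverse event reporting without reference to the table (Protocol 10.1.1; SAP 4.6.1). All of this stands, and it keeps the point minor.

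Second, the arithmetic bites only for a child with high resting HR or low resting BP, and the documents give no resting values. That also stands. The population extends to just under 12 years and 40 kg, so middle values cannot be excluded, and at HR mean 90 or SBP mean 110 the rates are low.

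Third, the laboratory comparison is imperfect: in the fixed-threshold rows the reference range takes over only when it is more extreme, which relaxes the limit and is not an age adjustment. This is fair. The comparison shows that the table can vary its limits, not that a paediatric rule was left out.

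A reader might go further and infer that the PCSV listing would consist largely of stable small children, or that large HR falls and BP rises would go unseen. The documents do not support either. The change condition still screens: even at the top assumed rate of 27.5%, about 72% of stable children get no high-HR flag. An unflagged change still appears in the full listing. Nor does the creatinine limit labelled for adults prove that the vital-sign rows were taken from an adult list; the documents do not state their source.

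**Conclusion.** The point holds, at minor severity. The single set of limits is read directly from Appendix 10.1. The break-even baselines (HR 100, SBP 115, DBP 55) and the distances to the opposite flags (more than 85 bpm, 70 mmHg, 55 mmHg) follow from it without outside data, provided that baseline is recorded. Below HR 100 or above SBP 115 and DBP 55, the absolute limit still works.

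The flag rates are illustrations. They rest on assumed resting means and SDs, normal readings and two post-baseline assessments, and correlation between the pre-dose and 1-hour readings lowers them. No count of children is possible: SAP section 1 reports that enrolment was paused, and the actual group sizes are not given.

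The consequence is limited to the descriptive vital-sign PCSV flags and the listing that they select. The primary PK endpoint is untouched.

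**What to change.** Before database lock, replace the single HR, SBP and DBP rows of Appendix 10.1 with pre-specified age-banded limits, cite their source, and keep the change-from-baseline condition in each row. The values are for the sponsor to choose and justify; the documents do not supply them.

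The cost is a revised appendix and some programming, with no new assessments. SAP 4.1 lists age in years, so bands for infants would need age in months, which is assumed to be derivable. The table would also depart from any standard list that the sponsor uses across studies.

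The missing-baseline rule can stay. It lets the absolute limit decide alone, but pre-dose vital signs are scheduled, so it should rarely apply, and suitable limits would remove most of the worry. The adult label on the creatinine limit is a separate, optional clarification; the 30% and 100% change criteria in that row operate regardless.
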